Assessments are described in Section 10, and associated timing for each assessment is provided in [Table 4](#), [Table 5](#), and [Table 6](#) for SAD, OL-RD, and DB-RD cohorts, respectively.

Table 4: Schedule of Events for the Single Ascending Dose Cohorts

Day (D) / Week (W) Visit Window Relative to Baseline	Screening ^a	BL	Follow-up Period						EOS I (D90) ^{b/} ET ^c
		D0	D1	D4	D7	D14	D21	D28	
Informed consent	X				± 1 day				
Inclusion/exclusion	X	X							
Drug Administration		X							
General Assessments									
General & GSD III-specific medical history	X								
COVID-19 testing	X								
Demographics	X								
Physical exam ^d	X	X ^e	X						X
Vital signs	X	X ^f	X	X	X	X	X	X	X
Height	X								
Weight	X	X ^e							X
Adverse events	X	X	X	X	X	X	X	X	X
Concomitant medications	X	X	X	X	X	X	X	X	X
Pregnancy	X	X ^e							X
ATX95			X ^g	X ^g	X ^g	X ^g	X ^g	X ^g	
AGL mRNA			X ^g	X ^g	X ^g	X ^g	X ^g	X ^g	
Anti-drug antibodies			X ^e				X		X
Hepatitis B & C	X								
Hemoglobin A1C	X								
Serum CH50, AH50, sC5b-9, & IL-6			X ^h	X			X		
Plasma fibrinogen & d-dimer			X ^h	X			X		
Hematology	X	X ^e	X	X	X	X	X	X	X
Chemistry ⁱ	X	X ^e	X	X	X	X	X	X	X
Urinalysis ^j	X	X ^e	X	X	X	X	X	X	X
Serum CRP			X ^e	X	X	X	X	X	X
Liver									
Liver MRI ^k	X								
Liver MRS ^k	X								
FibroScan or ultrasound elastography	X								
PT/INR ⁱ	X	X ^e	X		X				X
Serum HDL & LDL ^l	X	X ^e							

Day (D) / Week (W)	Screening ^a	BL	Follow-up Period						EOS I (D90) ^{b/} ET ^c		
		D0	D1	D4	D7	D14	D21	D28			
Visit Window Relative to Baseline		-	-	-	± 1 day	± 2 days					
Cardiac											
Serum CK-M/B	X	X ^e									
Plasma BNP	X	X ^e									
Serum troponin I	X	X ^e									
ECG	X	X ^e	X						X		
Skeletal Muscle & Strength											
Serum CK	X	X ^e									
HHD	X	X ^e									
Clinician- & Patient-reported Outcomes											
PROMIS questionnaires & SF-36v2		X ^e									
GNEM-FAS expanded version		X ^e									
Nutrition diary	X ^m	X ^m	X ^m	X ^m	X ^m	X ^m	X ^m	X ^m	X ^m		
Exploratory Assessments											
Serum ketones	X	X ^e	X	X	X	X	X	X	X		
Serum biotinidase	X	X ^e									
CGM ⁿ	X ⁿ	X ⁿ	X ⁿ	X ⁿ	X ⁿ	X ⁿ	X ⁿ	X ⁿ	X ⁿ		
Urine Glc ^o	X	X ^e			X				X		
AGL variant analysis	X										
WBC, RBC, Serum & Plasma for Future Use ^o		X ^e			X			X	X		

Footnotes continue on the following page.

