^a Screening assessments can be done over the course of multiple days. There must be a minimum of 10 days between any assessments that are measured at both the Screening and the BL Visit.

^b At the Day 90 Visit, marking completion of the Follow-up Period, subjects can be rescreened for entry into the OL-RD cohorts. Subjects must sign informed consent to enter into OL-RD cohorts prior to rescreening. Only EOS I Day 90 Visit assessments are included in the table above; please refer to [Table 5](#) for assessments that should be performed for rescreening for OL-RD. If rescreening for OL-RD occurs in conjunction with the SAD EOS I Day 90 visit, assessments in common should not be duplicated.

^c In the event a subject has an ET, all efforts will be made to monitor the subject through the end of the study. At minimum, a safety follow-up phone call will occur within the 4 weeks following the subject's last treatment.

^d Complete physical exam is required at the Screening, BL, and EOS I/ET Visits. Targeted physical exams may be performed at the D1 Visit.

^e Assessments to be performed prior to dosing. The following assessments can be collected within a week prior to dosing, as long as there is a minimum of 10 days between assessments that are repeated at the Screening Visit and the Baseline Visit: HHD, PROMIS questionnaires, SF-36v2, and GNEM-FAS expanded version.

^f Refer to [Table 7](#) for the timing of vital sign assessments during dosing.

^g Refer to [Table 8](#) for details of PK sampling. Please note that sample collections are marked for D1, D4, D7, D14, D21, and D28 in this table ([Table 4](#)) corresponding to a sample collection 1, 4, 7, 14, 21, and 28 days after infusion of UX053 on D0 as outlined in the final rows of the first column in [Table 8](#).

^h Sample to be collected pre-dose and at the end of the infusion. Post-infusion blood samples should be collected in the opposite arm of the infusion to avoid dilution.

ⁱ Close monitoring is required for subjects who develop elevations in ALT > 3x ULN and > 2x their baseline value, or elevation in ALT > 3x ULN with INR > 1.5. This includes repeating liver enzymes and INR within 48 hours and consideration of additional diagnostic tests such as liver ultrasound ([Section 10.1.5](#)).

^j All efforts should be made for urine collections to be consistently taken from the first morning void.

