^k If feasible, glycoNOE imaging of the liver, may be collected at the time of the liver MRI. Liver MRS are only required at sites with capability. Scanning for liver MRS can be conducted immediately following the liver MRI.

^l A 3- to 4-hour fasting period is preferred, but not required, prior to blood collection for serum HDL and LDL. All efforts should be made to obtain samples for HDL and LDL consistently for a given subject.

^m The nutrition diary recordings should be recorded at least 3 consecutive days per week through Screening and for the 3 consecutive days in the week leading up to each subsequent visit.

ⁿ The subject will receive CGM and HHG devices and will be trained on proper use at the Screening Visit. The CGM device is intended to be worn continuously from the Screening Visit to the EOS I D90/ET Visit. If the CGM device alarm notifies a subject that their blood sugar is abnormally high or low or the subject suspects their blood sugar is abnormally high or low, the subject will need to check their blood sugar with a HHG device that will be provided by Ultragenyx during screening. When CGM data is being collected, all subjects will connect their CGM and HHG devices to a study-provided laptop weekly and upload CGM and HHG data. At remote visits, in conjunction with assessments performed by a home health nurse, the site will contact subjects by telephone or videoconference to confirm the CGM device is properly in use and data was uploaded; answer any questions regarding or help troubleshoot (if necessary) CGM device use; and review CGM data, HHG data (when applicable), and nutrition diary entries; outside of scheduled visits, these telephone calls will occur as needed. At in-clinic visits, a conversation between the site and the subject should occur to ensure CGM compliance and troubleshoot if needed.

^o Serum and plasma samples will be collected for future biomarker assessments yet to be determined.

Note: White columns indicate in-clinic visits (Screening, BL D0, D1, and EOS I D90/ET). Gray columns indicate visits conducted at home by a home health nurse in conjunction with a phone call as needed (D4, D7, D14, D21, and D28).

Note: Laboratory assessments included in chemistry, hematology, and urinalysis are provided in [Appendix 3](#).

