5.5. Risk Minimization

Several components of this FIH study are designed to mitigate the potential risks of study participation, including implementation of a DMC, 72-hour intervals between dosing of individual subjects within a given SAD cohort, a cautious dose escalation scheme, slow drug infusion rate, prespecified premedications, availability of rescue medications, continuous cardiorespiratory monitoring during infusions, and 24-hour observation post infusion to monitor for post infusion effects.

Dose escalation will occur only after safety data reviews by the DMC. The DMC consists of a panel of independent medical and scientific experts (Section 7.1 and Section 11.12). Standard

safety laboratory tests are collected immediately prior to dosing (all cohorts) and again approximately 24 hours after dosing and at Day 4 (SAD cohorts) and Day 7 (both SAD and RD cohorts) (Section 10.1.5). In addition, characterization of complement activation through classical and alternative pathways, cytokine release, fibrinogen, and d-dimer will be assessed predose and at the end of each infusion. Potential risks of UX053 treatment identified from available nonclinical data with UX053 and known risks associated with siRNA or mRNA LNP therapies (Section 5.4.1) will be monitored throughout participation in the SAD and RD cohorts. Subjects will be monitored in an inpatient or observational unit for 24 hours after the end of each infusion.

The starting dose of UX053, 0.05 mg/kg, is approximately CCI below the human equivalent dose (HED) for the no-observed adverse effect level (NOAEL) for repeat dosing in dogs, approximately CCI below the HED for the NOAEL for repeat dosing in rats, and approximately CCI below the HED for the NOAEL for repeat dosing in cynomolgus monkeys using CCI scaling to calculate HED. The relative dose increase becomes smaller with each subsequent cohort: after a CCI dose increase from Cohorts 1S to 2S to 3S, there is a CCI dose increase between cohorts 3S and 4S. For RD cohorts, sequential doses may be reduced for individual subjects or for entire cohorts based on emerging safety findings.

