7.1.4. Dose Rationale

The planned doses of UX053 (0.05, 0.10, and 0.20 mg/kg) aim to establish a safe dose of UX053 in adults with GSD III, as well as provide a preliminary PK and PD profile of UX053. These doses were chosen based on single-dose and repeat-dose pharmacology studies in mouse and dog models of GSD III, and RD toxicology and toxicokinetic studies in rats, cynomolgus monkeys, and Beagle dogs. The NOAEL in repeat-dose studies with 5 total doses of UX053 administered Q2W was **CCI** mg/kg in dogs, **CCI** mg/kg in rats, and **CCI** mg/kg in monkeys. The maximum tolerated dose (MTD) was **CCI** mg/kg in rats and **CCI** mg/kg in monkeys. The MTD in dogs is not known since higher doses were not evaluated with Q2W administration. The MTD in dogs with weekly dosing of UX053 is **CCI** mg/kg, but this short interval between doses is believed to promote an accumulation of toxicity that does not occur with Q2W dosing. Hence, the MTD in dogs may be greater than **CCI** mg/kg when UX053 is administered Q2W, but remains undetermined. **CCI**

Taken together, these PK and drug metabolism properties of the drug support 1:1 weight-based scaling from nonclinical species to humans, which is an approach endorsed by a cross-industry consortium of experts in oligonucleotide therapies, the Oligonucleotide Safety Working Group (Kornbrust, 2019; Marlowe et al., 2017). The FIH starting dose of 0.05 mg/kg is **CCI** less than the NOAEL in the most sensitive nonclinical species, the dog. The highest potential FIH dose of 0.30 mg/kg is **CCI** less than the dog NOAEL. Additional details regarding the use of weight-based scaling versus body-surface area scaling, as well as summaries of nonclinical studies with UX053 are available in the IB.

Sequential dosing with an interval of 72 hours between subjects' first dose within a cohort and a 2-week minimum review of data between cohorts was chosen to allow enough time to detect any potential TEAEs, including potential immune responses. In nonclinical studies, toxicities generally occurred soon after dosing and promptly resolved. The DB-RD cohorts will aim to achieve a steady state with Q2W dosing. The OL-RD cohorts will aim to evaluate a Q4W dosing regimen. Subjects will receive premedication prior to the treatment infusion to prevent hypersensitivity reactions, in line with previously established programs evaluating RNA therapeutics.

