10.1.5. Safety Laboratory Tests

Blood and urine samples will be collected for safety laboratory tests as specified in [Table 4](#), [Table 5](#), and [Table 6](#). Fasting is not required. For visits in which subjects are receiving study drug, laboratory samples will be collected prior to dosing. All efforts should be made for urine collections to be from the first morning void. Samples will be processed by a central lab to ensure consistency across study sites.

In addition to chemistry, hematology, and urinalysis, additional assessments to monitor safety include activation of the complement pathway, coagulation factors, and interleukin-6. As noted in [Table 4](#), [Table 5](#), and [Table 6](#), samples for complement pathway, coagulation factors, and interleukin-6 are collected pre- and post-infusion. Post-infusion blood samples should be collected in the opposite arm of the infusion to avoid laboratory artefacts. The full list of safety laboratory evaluations to be performed in this study are listed in [Appendix 3](#). All laboratory samples listed in [Appendix 3](#) will be processed by a central laboratory, except urine pregnancy.

The study site should indicate to laboratories if the subject is taking high dose biotin supplements (found in multivitamins, biotin supplements, and some supplements to promote hair, skin, and nail growth) to potential risk of assay interference (eg, troponin) ([FDA, 2019a](#)).

The Investigator (and/or Medical Monitor) may at his/her discretion perform additional laboratory tests for subject safety if a subject experiences an SAE or other AE that may warrant further follow up.

Close monitoring is required for subjects who develop elevations in ALT > 3x ULN and > 2x their baseline value, or elevation in ALT > 3x ULN with INR > 1.5. This includes repeating liver enzymes and INR within 48 hours and consideration of additional diagnostic tests such as liver ultrasound.

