10.4.1.4. Prothrombin Time/International Normalized Ratio

Blood will be collected for the measurement of prothrombin time (PT) and to calculate PT/INR to aid in the assessment of liver health at time points specified in [Table 4](#), [Table 5](#), and [Table 6](#). For visits in which subjects are receiving study drug, laboratory samples will be collected prior to dosing. Samples will be processed by a central lab to ensure consistency across study sites.

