APPENDIX 3. LABORATORY ASSESSMENTS

Chemistry	Hematology	Urinalysis	Additional Labs
Alanine aminotransferase (ALT)	Hematocrit	Appearance	Blood Collection:
Alkaline phosphatase (ALP)	Hemoglobin	Color	Alternative complement activity (AH50)
Amylase	Mean corpuscular hemoglobin (MCH)	pH	B-type natriuretic peptide (BNP)
Aspartate aminotransferase (AST)	MCH concentration (MCHC)	Specific gravity	Classical pathway complement activity (CH50)
Bicarbonate	Mean corpuscular volume (MCV)	Bilirubin	C-reactive protein (CRP)
Bilirubin (direct and total)	Platelet count	Creatinine	Creatinine kinase (CK)
Blood urea nitrogen (BUN)	Red blood cell (RBC) count	Glucose	Creatinine kinase-muscle/brain (CK-M/B)
Calcium	Reticulocyte count	Hemoglobin	D-dimer
Chloride	White blood cell (WBC) count	Ketones	Fibrinogen
Cholesterol (total)	WBC differential	Nitrite	Hemoglobin A1C
Creatinine	Basophil count (absolute and %)	Protein	High density lipoprotein (HDL)
Gamma-glutamyl transferase (GGT)	Eosinophil count (absolute and %)	Urobilinogen	Interleukin-6 (IL-6)
Glucose	Lymphocyte count (absolute and %)	Pregnancy (if applicable)	Ketones
Lactate dehydrogenase (LDH)	Monocyte count (absolute and %)		Low density lipoprotein (LDL)
Lipase	Neutrophil count (absolute and %)		Prothrombin time/international normalized ratio (PT/INR)
Magnesium	Complete blood count with differential (CBC/diff)		Troponin I
Phosphorus			Soluble complement 5b-9 (sC5b-9)
Potassium			Urine Collection:
Protein (albumin and total)			Glucose tetrasaccharide (Glc ₄)
Sodium			
Triglycerides			

Note: table does not include blood collection for PK (ATX95, *AGL* mRNA), anti-drug antibodies, *AGL* variant analysis, and serum and plasma for future use; these assessments are measured as specified in [Table 4](#), [Table 5](#), [Table 6](#), and [Table 8](#).

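### SAD cohorts: post-dose PT/INR is scheduled only at Days 1, 7 and 90, so an INR rise between Days 1 and 7 without a marked transaminase rise would be found only by discretionary testing

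*Protocol*

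**What the plan says.** **Schedule.** Protocol Table 4 marks PT/INR at Screening, pre-dose on Day 0, and then at Days 1, 7 and 90. The cells for Days 4, 14, 21 and 28 are blank. Chemistry and hematology are marked at every post-dose visit. The SAP's copy of the table (SAP 10.3), which still carries a Day 42 visit, marks PT/INR at the same three post-dose visits.

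**No other text adds a reading.** Protocol 10.4.1.4 collects blood "to calculate PT/INR to aid in the assessment of liver health at time points specified in" the schedule tables. Appendix 3 lists "Prothrombin time/international normalized ratio (PT/INR)" among the additional labs, outside the chemistry and hematology panels.

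**Extra INR.** Table 4 footnote i requires close monitoring, including a repeat INR within 48 hours, for "elevations in ALT > 3x ULN and > 2x their baseline value, or elevation in ALT > 3x ULN with INR > 1.5". Section 8.3.2 asks for a further INR when transaminases exceed both twice baseline and three times ULN. Otherwise, under Section 10.1.5, the investigator or Medical Monitor may order additional "laboratory tests for subject safety if a subject experiences an SAE or other AE that may warrant further follow up".

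**What depends on INR.** Section 5.4.1 names consumptive coagulopathy as a risk and prolonged PT/INR as one of its signs. Section 8.3.3 pauses the study when three subjects have INR above 1.5, with no ALT condition. Section 7.1 lets the DMC act on two weeks of data from two subjects, both for the next SAD cohort and, from Cohort 2S, for opening repeat dosing.

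**The concern.** The SAD cohorts are the first human exposure. Platelets and INR each have a three-subject pause rule. Platelets are read at every post-dose visit; INR is not read at Day 4 or Day 14. Mandatory reflex testing follows the transaminases, so it does not serve a rule that has no ALT condition.

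An INR rise that begins after Day 1 and has settled by Day 7, without a marked transaminase rise, would enter the pause count only if someone chose to order the test. The DMC could then decide on escalation without knowing of it. A later report could also read an absence of INR events as stronger reassurance than two readings in two weeks can give.

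**Working it through.** The plan states no figure on this point, so the check is a count of scheduled readings from Table 4, followed by the reach of the reflex rule.

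1. **Is the row readable?** The PT/INR row in Table 4 accounts for all nine columns, so its blanks are not an extraction shift. The SAP row accounts for all ten of its columns and has the same post-dose marks.

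2. **Whole follow-up.** Post-dose visits are Days 1, 4, 7, 14, 21, 28 and 90, that is 7. Chemistry and hematology: 7 of 7. PT/INR: 3 of 7.

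3. **Minimum DMC window.** Post-dose visits up to Day 14 are Days 1, 4, 7 and 14, that is 4. PT/INR is at 2 of 4. With Day 4 added it is 3 of 4; with Days 4 and 14 added, 4 of 4.

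4. **Longest nominal interval in the first week.** Now 7 − 1 = 6 days. With Day 4: 4 − 1 = 3 and 7 − 4 = 3 days.

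5. **Scheduled post-dose INR readings at a minimum DMC review (2 subjects).** Now 2 × 2 = 4; with Day 4, 2 × 3 = 6; with Days 4 and 14, 2 × 4 = 8.

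6. **Reach of the reflex rule.** The ALT-only limb of footnote i needs ALT above max(3, 2 × baseline) times ULN. Inclusion criterion 3 allows ALT up to 5 times ULN in the three months before baseline.
   - Baseline 2.5 × ULN: the threshold is max(3, 5) = 5 × ULN.
   - Baseline 5 × ULN: the threshold is max(3, 10) = 10 × ULN.

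   So at a baseline of 2.5 × ULN, an ALT above 3 and up to 5 × ULN leads to close monitoring only through the INR limb. That limb needs an INR result, and none is scheduled at Day 4 or Day 14. This is a narrow case, but it shows that the reflex does not replace a scheduled reading.

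**The case against.** The other side has several good points.

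- **No text is breached.** Section 5.5 has standard safety labs collected "again approximately 24 hours after dosing and at Day 4 (SAD cohorts) and Day 7 (both SAD and RD cohorts)". A reader might infer that leaving INR off Day 4 contradicts this. It does not: the section does not list PT/INR among those tests, and chemistry, hematology and urinalysis are all drawn on Day 4. This stands.
- **Other coagulation markers exist.** A reader might infer that Day 4 has no coagulation test at all. The "Plasma fibrinogen & d-dimer" row cannot settle this. As extracted, its marks fall under Days 1, 4 and 21. Its footnote (pre-dose and end of infusion) puts the first mark at Day 0, but that does not show that the other marks move too. These markers may give partial cover, and nothing here rests on them. They do not feed the INR count.
- **Onset is expected early.** Section 7.1.4 says that nonclinical "toxicities generally occurred soon after dosing and promptly resolved". This supports the Day 1 reading. It also means that a rise starting after Day 1 could be over by Day 7, but the documents do not show that INR behaves in this way. The scenario is plausible, not demonstrated.
- **The pause count needs three subjects.** Two subjects cannot reach it on any schedule. That is right. The count is cumulative and study-wide, so a missed reading in one cohort lowers the count carried into the next, but the rule is not disabled.
- **Existing cover is real.** ALT and platelets are read at every visit, a marked transaminase rise brings an INR, subjects are told to seek care for unusual bleeding or bruising (9.1.4), and chronic coagulopathy and INR-altering drugs are excluded (8.2). What remains uncovered is an isolated, transient INR rise.
- **The double-blind repeat-dose cohorts are not a fair comparison.** The amendment summary puts PT/INR at all their treatment and follow-up visits for early detection of coagulopathy and liver injury. That shows the value placed on INR. It does not show that SAD is monitored less closely overall, because Table 6 has no Day 1 column.

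**Conclusion.** The gap is real and modest. Scheduled post-dose INR covers 2 of the 4 visits up to Day 14 and 3 of 7 overall, with a 6-day interval in the first week. The compound liver rule in Section 8.3.3 is largely protected at Days 4 and 14, because chemistry is drawn then and a marked transaminase rise triggers an INR. The exposed rule is the INR count that has no ALT condition.

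The conclusion rests on the PT/INR row alone. It assumes no particular time course for INR, and it claims neither a conflict within the protocol nor an inoperative stopping rule. It is best treated as a cheap improvement to the monitoring of a named risk. SAP Section 8 records termination after Cohorts 1S and 2S (four subjects each), which limits the practical effect to any further SAD dosing and to how the completed data are described.

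**What to change.** Mark PT/INR at Day 4 in Table 4. The notes to the table list "visits conducted at home by a home health nurse in conjunction with a phone call as needed (D4, D7, D14, D21, and D28)", and Day 7 is already a home visit with PT/INR, so no new visit is needed. Optionally mark Day 14 as well, so that INR is read at the end of the minimum DMC window. No threshold or stopping rule has to change.

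The cost is one extra coagulation tube and one central-laboratory test per added visit, with slightly more blood drawn. Each SAD subject already has 5 scheduled PT/INR tests (Screening, Day 0, Days 1, 7 and 90), so 6 subjects have 6 × 5 = 30. Day 4 adds 6 × 1 = 6; Days 4 and 14 add 6 × 2 = 12. For the 8 subjects enrolled, the additions would have been 8 or 16.

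For subjects already dosed, the study report should state that post-dose INR was scheduled only at Days 1, 7 and 90, so that an absence of recorded INR rises is read in that light.
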